Primary	To assess the real-world implementation of superficial hyperthermia using CE marked water-filtered infrared A (wIRA) in addition to palliative SOC radiotherapy	
 1. Quantitative: the total number and types of cancer patients successfully treated with the combination of superficial hyperthermia and palliative radiotherapy. 2. Descriptive: to evaluate the real-world implementation by the NASSS (non-adoption, abandonment, scale-up, spread, and sustainability) framework using NASSS-CAT (complexity assessment tool)
Secondary	1. To assess the best objective response rate (ORR) of the lesion(s) treated with combination of superficial hyperthermia with palliative radiotherapy	
 1. Best ORR: Defined as the proportion of patients achieving either a Complete Response (CR) or a Partial Response (PR). Complete Response (CR): Disappearance of all target lesions.

		Partial Response (PR): $\geq 30\%$ decrease in the sum of diameters of target lesions, taking as reference the baseline sum diameters.
	2. To determine the tolerability and safety profile of superficial hyperthermia in patients receiving SOC palliative radiotherapy	2. Local serious adverse events (SAEs) will be assessed by Common Terminology Criteria for Adverse Events (CTCAE) version 5.0.
	3. To evaluate the median local and global progression-free survival (PFS) and median overall survival (OS) of patients at 12 months after the last patient is recruited	
3. Patients not experiencing an event (progression or death) will be censored at the time of the final analysis at the date last known to be alive and progression-free.
 
Local: refer to the lesions treated by radiotherapy +/- superficial hyperthermia.
 
Global: local and distant (non-treated lesions)
 
PFS: Defined as the time from baseline to the first documented progressive disease (PD) or death from any cause, whichever occurs first.
 
Progressive disease (PD): At least a 20% increase in the sum of diameters of target lesions or development of new lesions, with the date of progression recorded by a clinician in the patient's hospital records.
 
OS: The time from the start of treatment to death from any cause.

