treatments such as radiotherapy and chemotherapy at many cancer centres across the world, its use has not been established in NHS settings. The main difficulties in introducing its use into routine clinical practise is the lack of expertise in its use as well as the lack of availability of clinically approved hyperthermia machines at any UK cancer centre. Guys Cancer Centre is the first centre nationally to introduce a CE marked hyperthermia machine (hydrosun®-TWH1500) for patient use in the NHS.

Patients presented with inoperable/recurrent disease usually have limited prognosis and any associated symptoms such as pain, discharge, infection, and bleeding significantly affect their quality of life. Several publications support the clinical use of hyperthermia with palliative radiotherapy in multiple tumour types (19). Datta et.al provides a summary of the clinical outcomes of 38 clinical trials across various tumour sites including breast, head and neck and skin melanoma comparing radiotherapy (1717 patients) versus thermoradiotherapy (1761 patients) and reported an overall clinical response of 54.9% in thermoradiotherapy groups vs 38.9% in the radiotherapy alone group (odds ratio: 2.3, 95% confidence interval 1.95–2.72, $p < 0.001$) (19). In a randomised phase 3 trial of patients with superficial measurable tumours treated with either radiotherapy alone or radiotherapy followed immediately by hyperthermia (42.5 degrees C, 45-60 min), a better CR rate was observed with a combination of radiotherapy and heat (62 and 67%) compared with irradiation alone (40 and 0%) in tumours less than 3 cm in diameter in the breast, trunk, and extremities despite no difference in overall CR between the two arms (20).

In head and neck cancer, a systematic review and meta-analysis comparing the efficacy of hyperthermia plus radiotherapy over radiotherapy alone showed an overall CR of 62.5% in the combination treatment versus 39.6% in the radiotherapy alone group (21). Moreover, a systematic review investigating the role of hyperthermia in the treatment of local recurrent breast cancer (LRBC) showed that the combination of hyperthermia with radiotherapy achieved a complete response rate of 60.2% compared to 38.1% for radiotherapy alone (22). However, most of the previous evidence is based on older hyperthermia and radiotherapy techniques, which have been disregarded by many oncologists as non-comparable to current standard of care.

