Secondary	
1. To assess the best objective response rate (ORR) of the lesion(s) treated with (1) combination of superficial hyperthermia with palliative radiotherapy; (2) radiotherapy alone
 
2. To determine the tolerability and safety profile of superficial hyperthermia in patients receiving SOC palliative radiotherapy
 
3. To evaluate the median local and global progression-free survival (PFS) and median overall survival (OS) of patients at 12 months after the last patient is recruited
 
Local: refer to the lesions treated by radiotherapy +/- superficial hyperthermia.
 
Global: local and distant (non-treated lesions)
 
4. To assess the median duration of objective response and locoregional control rates of the treated lesion(s) at 6 and 12 months
	
1. Best ORR: Defined as the proportion of patients achieving either a Complete Response (CR) or a Partial Response (PR).
 
Complete Response (CR): Disappearance of all target lesions.
 
Partial Response (PR): ≥ 30% decrease in the sum of diameters of target lesions, taking as reference the baseline sum diameters.
 
2. Local adverse events (AEs) and adverse reactions (ARs) will be assessed by Common Terminology Criteria for Adverse Events (CTCAE) version 5.0.
 
3. PFS: Defined as the time from baseline to the first documented progressive disease (PD) or death from any cause, whichever occurs first.
 
PD: At least a 20% increase in the sum of diameters of target lesions or development of new lesions, with the date of progression recorded by a clinician in the patient's hospital records.
 
OS: The time from the start of treatment to death from any cause.
 
Patients not experiencing an event (progression or death) will be censored at the time of the final analysis at the date last known to be alive and progression-free.
 
4. Duration of Objective Response: Defined as the time from the first documented Complete Response (CR) or Partial Response (PR) to disease progression or metastasis.

		Locoregional Control Rate: The proportion of patients whose primary tumour site remains free from progression.

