○ Study design

This is a prospective study to assess the real-world implementation of superficial hyperthermia (wIRA) in combination with SOC palliative radiotherapy in cancer patients not suitable for radical treatment and have superficial lesion(s) suitable for wIRA treatment. All eligible patients will be recruited in the study by the clinical team following discussion with the chief investigator or the designated clinical sub-investigator. Patients will be consented for palliative radiotherapy as per standard treatment. The radiotherapy dose delivered will be clinician's choice based on SOC table 1 schedules.

Table 2: Schedule of radiotherapy and hyperthermia

Palliative radiotherapy (Primary vs Re-irradiation)	Dose	Fractions	Radiotherapy	Hyperthermia
Primary or Re-irradiation (previous standard palliative dose)*^	27Gy	6	Twice per week	Once per week
Re-irradiation (previous radical dose)*^	20Gy	5	Once a week (up to 5 weeks)	Once per week
Primary or Re-irradiation (previous standard palliative dose)*^	20Gy	5	Daily over 1 week	Twice per week
Re-irradiation (previous radical or palliative dose)*^	20Gy	10	Daily over two weeks	Twice per week
Primary or Re-irradiation (previous standard palliative dose)*^	36Gy	6	Once a week	Once per week

*The combined dose from previous RT and proposed RT fractionation will not exceed tolerance dose for critical organs (assuming recovery if necessary, as per routine clinical practice). If completing the full radiotherapy schedule would result in exceeding the tolerance dose to critical organs, treatment may be administered on a weekly basis until the tolerance threshold is reached.

[^]The combined dose from previous RT and proposed RT fractionation will not exceed tolerance dose for critical organs (assuming recovery if necessary, as per routine clinical practice) and the combined dose to soft tissue of the irradiated area will not exceed 70Gy in equivalent 2Gy per fraction (without assuming recovery).

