The patients will receive hyperthermia either once a week or twice a week (as listed in Table 1) using hydrosun® TWH1500 with palliative radiotherapy. The patients will receive hyperthermia treatment for 1 hour before going for palliative radiotherapy as per standard of care. For patients who will undergo 27Gy/6#, they will receive hyperthermia once a week for three weeks during the course of palliative radiotherapy. For patients undergoing 20Gy/5# over five weeks or 36Gy/6# over six weeks, they will receive hyperthermia once a week. For patients undergoing 20Gy/5# over one week or 20Gy/10# over two weeks, they will receive hyperthermia two times per week during their treatment.

Most of the HNSCC patients will be suitable for palliative pembrolizumab (if the tumours are CPS \geq 1) and the cSCC patients will be suitable for cemiplimab if they have an ECOG performance status \leq 1. We would aim to start palliative pembrolizumab within 6 weeks (+/- 2 weeks) of completing palliative radiotherapy if patients are deemed to be suitable and fit for this treatment as part of the standard of care. LRBC patients will undergo systemic treatments as per standard of care according to their previous treatment histories and breast cancer subtypes.

Patients will be assessed during their treatment for toxicities, and rate of adverse events will be assessed by CTCAE version 5.0. Follow-ups and assessment of response will be done as per standard of care.

When appropriate, we will aim to collect biological samples from each patient for translational research (see below) including archival tumour sample, fresh tumour biopsy or resection sample when available, blood samples at different time intervals before, during and after their treatments as well as saliva and mouth swab at the same time points when appropriate. The samples will be analysed to further assess the tumour microenvironment, the peripheral immune response and to identify predictors of treatment response.

For all patients, blood samples will be collected at baseline (at time of consent), before the first round of hyperthermia/radiotherapy treatment*, after the first round of hyperthermia/radiotherapy

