In line with the study sponsor conditions and HRA guidance, if a SAE is discovered and thought to be related to superficial hyperthermia (+/- SOC palliative radiotherapy), the CI will immediately report upon knowledge of the event to the R&D Department within 24 hours. If the SAE is considered to be related to superficial hyperthermia (+/- SOC palliative radiotherapy) and unexpected, it will also be reported to the relevant REC committee within 15 days of the CI becoming aware of the event. The HRA defines SAEs as related to the study if it involves the administration of any of the research procedures and unexpected as in that it was not listed in the protocol as an expected occurrence. If the CI deems a SAE to be disease-related and not related to the superficial hyperthermia (+/- SOC palliative radiotherapy), the SAE will be documented but only reported in the final study report. Therefore, only SAEs that are localised to the site of hyperthermia (local adverse events) will be reported. Participants will be monitored for SAEs for 6 weeks after completion of radiotherapy. All documentation relating to SAEs will be kept in the Trial Master File.

12. Compliance and withdrawal

- **Subject compliance**

We will monitor the percentage of approached participants who consent to taking part in the study during the first year of recruitment.

- **Withdrawal/dropout of subjects**

We will monitor the percentage of participants who withdraw consent or drop out from the study after taking part. We will replace the subjects if necessary to make up the total target number of patients (n=30) as long as this is within the recruitment period.

- **Protocol compliance**

The patients will undergo routine treatments as per standard of care.

13. Data

- **Data management**

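### Section 11 triggers SAE reporting by relatedness but then limits it to the heated site, and the safety endpoint is local SAEs in the synopsis but local AEs and ARs in Table 1

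*Protocol*

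**What the plan says.** **SAE reporting (Protocol, Section 11, Procedures for Recording and Reporting Adverse Events).** One paragraph sets the rules.

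- The first sentence imposes the 24-hour report to R&D "if a SAE is discovered and thought to be related to superficial hyperthermia (+/- SOC palliative radiotherapy" (the closing bracket follows in the text). The second adds the REC, within 15 days, for events that are related and unexpected. Neither names a site.
- The fourth sentence deals with an SAE that the chief investigator judges disease-related and unrelated to treatment: "the SAE will be documented but only reported in the final study report".
- The fifth is introduced as a consequence of what precedes it: "only SAEs that are localised to the site of hyperthermia (local adverse events) will be reported".

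**Safety endpoint.** Secondary objective 2 (tolerability and safety) has the same wording in the synopsis (Section 4) and in Table 1 (Section 6). The endpoints beside it differ.

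- Synopsis: "Local serious adverse events (SAEs) will be assessed by Common Terminology Criteria for Adverse Events (CTCAE) version 5.0".
- Table 1: "Local adverse events (AEs) and adverse reactions (ARs) will be assessed by Common Terminology Criteria for Adverse Events (CTCAE) version 5.0".
- Section 7, Study design: "Patients will be assessed during their treatment for toxicities, and rate of adverse events will be assessed by CTCAE version 5.0".

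**The concern.** The reporting paragraph changes its criterion halfway. It starts with causation and ends with anatomy, and presents the second as if it followed from the first. An SAE attributed to treatment but arising outside the heated area must be reported under the opening sentences and is excluded under the closing one. The conflict runs in the unsafe direction, because the narrower sentence gives a literal reason to hold back a treatment-related event from R&D and the REC.

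The endpoint conflict affects the final safety result. Local SAEs and all local AEs and ARs are different sets of events, and either could be presented as the protocol's safety endpoint. The objective is tolerability. An endpoint confined to serious events would leave out non-serious burns and blisters, which are the kind of local reaction that Section 11 itself discusses when it reviews earlier hyperthermia experience.

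Reporting rules and endpoint definitions belong in the protocol, so neither matter can be left to a separate analysis plan.

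**Working it through.** The protocol states no figure on this point and there is none to reproduce. The check sets the texts side by side.

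**Step 1. Reporting rules, by cause and site.** The relatedness rules are the first, second and fourth sentences of the Section 11 paragraph. The site rule is the fifth. The word *only* in the site rule is a restriction: it removes SAEs away from the heated site but does not require that every SAE at the heated site be reported.

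| SAE | Relatedness rules | Site rule, if it concerns expedited reports | Site rule, if it concerns any report |
|---|---|---|---|
| Related, heated site | R&D; REC if unexpected | Allowed: agree | Allowed: agree |
| Related, elsewhere | R&D; REC if unexpected | Excluded: **conflict** | Excluded: **conflict** |
| Disease-related, heated site | Final report only | Not required: agree | Allowed: agree |
| Disease-related, elsewhere | Final report only | Not expedited: agree | Excluded: **conflict** |

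The conflict is in 1 of 4 combinations on the expedited reading and in 2 of 4 on the any-report reading. The related SAE away from the heated site is in conflict on both.

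**Step 2. Could that combination be empty by design?** The two rules would agree on related SAEs only if every related SAE arose at the heated site. No section says so. The trigger covers hyperthermia with or without radiotherapy, and Section 11 notes that heat can sensitise to radiotherapy. The Table 2 footnotes limit cumulative dose to structures other than the lesion: "The combined dose from previous RT and proposed RT fractionation will not exceed tolerance dose for critical organs". That is a radiotherapy safeguard and not evidence that heating causes distant harm. It does show that the combined treatment is not assumed to act on the lesion alone. The combination may be uncommon, but the protocol does not rule it out.

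**Step 3. Endpoint 2, by source.**

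| Source | Events counted | Non-serious local burn or blister counted? |
|---|---|---|
| Synopsis, Section 4 | Local SAEs | No |
| Table 1, Section 6 | Local AEs and ARs | Yes |
| Study design, Section 7 | Rate of adverse events, limited neither to serious nor to local | Yes |
| Section 11, site rule | SAEs, which the bracket labels local adverse events | No |

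Table 1 and Section 7 both include non-serious events; the synopsis does not. The bracket in Section 11 blurs the two terms further by naming SAEs as local adverse events. All four are current text, and no sentence gives one of them precedence.

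**Step 4. Size.** Counting affected events would need a rate of related SAEs, the share of them outside the heated area, and a rate of non-serious local reactions. The protocol states none of these for this study, so no number is given.

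**The case against.** The best defence of the Section 11 sentence is that it is a loose summary and not a rule. The Introduction describes local heating as sparing, or nearly sparing, the normal tissue around the tumour. Section 11 expects no SAEs from hyperthermia alone. Authors with this in mind would naturally treat related and local as the same thing. The first two sentences are specific duties with deadlines, tied to sponsor conditions and HRA guidance. The chief investigator reports, and Section 14 has the study start at a single site. A summary sentence is unlikely to displace those duties in practice.

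Much of this stands. It explains how the sentence came to be written and suggests that the conflict will seldom arise. It does not remove it. The trigger includes harm from the combination with radiotherapy, and the sentence is worded as an exclusion.

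The defence also disposes of two stronger readings.

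- A reader might infer that the site rule forces expedited reporting of disease-related SAEs at the heated site, since the tumour is what is heated and the Introduction says that "any associated symptoms such as pain, discharge, infection, and bleeding significantly affect their quality of life". The text does not support this. A restriction to the heated site creates no duty to report everything there, and the fourth sentence still sends such events to the final report only.
- A reader might use the 30% figure for thermal blisters in Section 11 to size the endpoint gap. That figure is an increase reported by one study using older techniques. It is not an incidence and gives no expected count here.

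On the endpoint, the defence is that the synopsis line is simply out of step with Table 1 and Section 7. That is probably so, and it is a reason to correct the line.

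**Conclusion.** Both inconsistencies hold as written. In Section 11 the site rule does not follow from the relatedness rules. Read literally, it excludes treatment-related SAEs outside the heated area, which the same paragraph requires to be reported. If reporting is taken to include the final report, it also contradicts the fourth sentence for disease-related SAEs elsewhere. For the safety endpoint, the synopsis and Table 1 define different sets of events for the same objective, and only the Table 1 wording covers non-serious local toxicity.

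The conclusion rests on the wording alone and on no assumed event rate. A reader might go further and infer that related SAEs will in fact be withheld, or that a material number of events is affected. The documents do not support either: the specific reporting duties remain in force, and there is no rate from which to calculate. These are drafting faults in operative text, with a possible safety consequence, and should be corrected at the next amendment.

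**What to change.** 1. **Section 11.** Replace the fifth sentence with: *SAEs related to hyperthermia or its combination with radiotherapy, at any site, are reported as above; all other SAEs are documented and listed in the final study report.* The bracket equating local SAEs with local adverse events goes with it.
2. **Synopsis, secondary endpoint 2.** Copy the Table 1 wording (local AEs and ARs by CTCAE version 5.0) and state that SAEs are listed separately.
3. **Add no limit to the treatment period.** Table 1 sets none, and Section 7 says when patients are assessed without defining the endpoint by it. For 20 Gy in 5 daily fractions, such a limit would end AE capture after about one week and lose later local reactions, although the schedule of events has medical-record monitoring at 6 weeks, 12 weeks and 12 months.

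The cost is one sentence and one synopsis line in the next amendment. No visit or assessment is added, since Section 7 already calls for adverse event assessment and Section 11 for SAE monitoring and documentation. The downside is possibly a few more expedited reports to R&D and the REC.

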3. LRBC

- i) Locally recurrent breast cancer with previous radiotherapy treatment (re-irradiation)

- **Primary objective:**

1. To assess the real-world implementation of superficial hyperthermia [using CE marked water-filtered infrared A (wIRA) machine] in addition to palliative SOC radiotherapy

- **Secondary objectives:**

1. To assess the best objective response rate (ORR) of the lesions treated with the combination of superficial hyperthermia (wIRA) and palliative radiotherapy
2. To determine the tolerability and safety profile of the combination treatment of superficial hyperthermia (wIRA) and palliative radiotherapy
3. To evaluate the median progression-free survival (PFS) and overall survival (OS) of patients
4. To assess the median duration of objective response and locoregional control rates at 6 and 12 months
5. To assess patient-reported outcome measures (PROMs) and quality of life (QoL) of patients using the European Organization for Research and Treatment of Cancer (EORTC) Quality of Life Core Questionnaire (QLQ-C30) and head and neck module (QLQ-H&N35)
6. To assess the differences in the efficacy between the lesion(s) treated with radiotherapy with hyperthermia with the lesion(s) treated with radiotherapy alone in those patients with at least 1 additional lesion that is not suitable for treatment with hyperthermia
7. To compare clinical outcome of patients treated with combination of superficial hyperthermia and radiotherapy who may or may not undergo subsequent immunotherapy with the retrospective data of historical cohorts

- **Exploratory objectives/translational research:**

Collection of samples such as archival tumour sample, fresh tumour biopsy/resected sample when available, blood (PBMC), and saliva, for translational research (see below).

- **Table 1: Objectives and endpoints**

	Objectives	Endpoints
--	-------------------	------------------

Primary	To assess the real-world implementation of superficial hyperthermia using CE marked water-filtered infrared A (wIRA) in addition to palliative SOC radiotherapy as part of their standard of care (SOC)	
1. Quantitative: the total number and types of cancer patients successfully treated with the combination of superficial hyperthermia and palliative radiotherapy.
 
2. Descriptive: to evaluate the real-world implementation by the NASSS (non-adoption, abandonment, and challenges to scale-up, spread, and sustainability) framework using NASSS-CAT (complexity assessment tool) ⁵

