This is a real-world implementation study, and the patients participated in this study will undergo superficial hyperthermia in addition to SOC palliative radiotherapy. Hyperthermia treatment has not shown to significantly increase acute or late toxicities compared to radiotherapy alone. In a summary of the clinical outcomes of 38 clinical trials across various tumour sites using hyperthermia did not report any significant increase in reported acute or late toxicity with the addition of hyperthermia (19). Similarly, in a systematic review of the use of hyperthermia in addition to radiotherapy for head and neck cancer (20), did not report any worsening toxicities from the addition of hyperthermia, apart

from one study reporting a 30% increase of thermal blisters however both older radiotherapy and hyperthermia techniques have been used (22). The Hydrosun system has been evaluated in superficial breast cancer re-irradiation with no acute grade 2-4 toxicities been observed, including no burning with blistering (18). We will collect safety profile data from the patients undergoing superficial hyperthermia with SOC palliative radiotherapy in this study.

- **Procedures for Recording and Reporting Adverse Events**

No serious adverse events (SAEs) are expected to occur due to hyperthermia alone, but it can sensitize radiotherapy. For patients undergoing palliative radiotherapy and hyperthermia, they will be followed up by their treating clinicians as per normal practice.

The HRA gives the following definitions for Safety Reporting (Research other than Clinical Trials of Investigational Medical Products (CTIMPs)) for UK Health Departments' Research Ethics Service (RES):

Serious Adverse Event (SAE) is defined as an untoward occurrence that:

- a) Results in death; or
- b) Is life-threatening; or
- c) Requires hospitalization or prolongation of existing hospitalization or
- d) Results in persistent or significant disability or incapacity; or
- e) Consists of a congenital abnormality or birth defect; or
- f) Is otherwise considered medically significant by the investigator.

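### Planned safety collection ends 6 weeks after radiotherapy, so the trial will give no systematic rate of late local toxicity although its safety objective is not limited to acute effects

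*Protocol*

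**What the plan says.** **The objective.** Section 6 gives secondary objective 2 as "To determine the tolerability and safety profile of the combination treatment of superficial hyperthermia (wIRA) and palliative radiotherapy". The synopsis and Table 1 word it as "To determine the tolerability and safety profile of superficial hyperthermia in patients receiving SOC palliative radiotherapy". Neither restricts it to acute effects.

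**The endpoint.** The synopsis has "Local serious adverse events (SAEs) will be assessed by Common Terminology Criteria for Adverse Events (CTCAE) version 5.0". Table 1 has "Local adverse events (AEs) and adverse reactions (ARs) will be assessed by Common Terminology Criteria for Adverse Events (CTCAE) version 5.0". The two differ in scope, and neither states a collection period.

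**When toxicity is looked for.** Section 7 states: "Patients will be assessed during their treatment for toxicities, and rate of adverse events will be assessed by CTCAE version 5.0". Section 11 states: "Participants will be monitored for SAEs for 6 weeks after completion of radiotherapy". No section sets a later toxicity assessment.

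**What Section 11 says about the risk.** On earlier evidence: "Hyperthermia treatment has not shown to significantly increase acute or late toxicities compared to radiotherapy alone". On mechanism: "No serious adverse events (SAEs) are expected to occur due to hyperthermia alone, but it can sensitize radiotherapy".

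**What continues afterwards.** The schedule of events (numbered 5.1, within Section 7) marks medical record monitoring at every visit from baseline to 12 months after hyperthermia and radiotherapy. Section 13 lists what is extracted from the record after treatment: treatment details, response, progression and survival.

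**The concern.** The plan measures benefit and harm over very different periods. Duration of response and locoregional control are assessed at 6 and 12 months. Planned collection of harm ends at 6 weeks.

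The protocol's own content makes the later period relevant. It treats late toxicity as a category of its own, names radiosensitisation as the mechanism, and includes re-irradiation in all three disease cohorts, including after a previous radical dose (Table 2). The device-specific finding quoted in Section 11 concerns acute toxicity in breast re-irradiation, and Section 5 doubts whether the breast experience carries over to HNSCC or cSCC.

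A report of few or no local SAEs could therefore be read as an answer to the whole objective when it covers only the early part of follow-up.

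**Working it through.** The protocol has no power calculation (Section 14) and no safety figure to reproduce. The check is the coverage of the window, followed by an illustration.

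**Inputs from the protocol**
- SAE window: 6 weeks after radiotherapy ends (Section 11).
- Radiotherapy course: 1, 2, 3, 5 or 6 weeks (Table 2 and the text after it).
- Last scheduled record review: 12 months after treatment, taken as 52 weeks (schedule of events).
- Sample size: 15 to 20 per disease cohort, up to 60 in total (Section 8).

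**Coverage**
- Share of post-treatment follow-up inside the window: 6/52 = 11.5%.
- Share with no stated safety collection: 46/52 = 88.5%.
- Closing time counted from the start of treatment: 1 + 6 = 7 weeks for the shortest course, 6 + 6 = 12 weeks for the longest.

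**What a clean result would establish.** With zero events in n patients, the one-sided 95% upper bound is 1 − 0.05^(1/n):
- n = 60: 4.9%
- n = 20: 13.9%
- n = 15: 18.1%

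These bounds apply only to events up to week 6.

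**Illustration under assumptions.** The protocol gives neither an onset time nor a rate for late local events. Assume exponential onset with median m weeks, so F(t) = 1 − 0.5^(t/m). The share of 12-month events that begin by week 6 is F(6)/F(52):
- m = 13: 0.274/0.9375 = 29%
- m = 26: 0.148/0.75 = 20%
- m = 52: 0.077/0.5 = 15%

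Assume also a true 12-month rate of 5%, complete follow-up and no competing deaths. The chance of at least one event is 1 − (1 − 0.05 × share)^n, with share = 1 for the full 12 months:

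| n | Over 12 months | To week 6, m = 13 | m = 26 | m = 52 |
|---|---|---|---|---|
| 60 | 0.95 | 0.59 | 0.45 | 0.37 |
| 20 | 0.64 | 0.26 | 0.18 | 0.14 |

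If the assumed rate is 10% and n = 60, the figures are 0.998 over 12 months against 0.83, 0.70 and 0.61. If late events begin only after week 6, the window sees none of them. Competing deaths in this palliative population would lower the 12-month column, so the contrast shown is on the high side.

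**The case against.** The strongest case against is that the 6-week sentence governs SAE monitoring alone.
- The AE and AR endpoint in Table 1 has no time limit. Section 11 also promises safety data without one.
- The rule for reporting related SAEs is triggered by discovery, whenever that happens.
- Record monitoring runs to 12 months, and the Section 7 sentence on toxicity during treatment does not say only then.
- PROMs, which Section 7 links to radiotherapy toxicity, run to 12 weeks.

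A reader might infer that the trial cannot detect late toxicity, or is bound to report none. The documents do not support that: a related local SAE found at the 12-month review could be reported. What remains is that none of these routes is a planned late assessment. PROMs are not CTCAE-graded local events, and events that come to light by chance give no rate with a known denominator.

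The window may also have a sensible reason. Section 7 aims to start pembrolizumab within 6 weeks, give or take 2, of completing radiotherapy, so the window closes about when a confounding therapy begins for many HNSCC patients. The protocol does not give this as its reason. It bears on attribution and not on whether events should be recorded.

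Finally, no endpoint promises late toxicity. The sentence naming it summarises earlier studies, and safety is secondary in an implementation study. That makes this a weakness of design and not an outright contradiction.

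**Conclusion.** The point holds as a gap in planned collection. As written, the trial can describe local SAEs up to 6 weeks after radiotherapy, 11.5% of the year to the last record review. It cannot report a late local toxicity rate. The coverage figures follow from the protocol alone. The detection probabilities rest on an assumed event rate and assumed onset times, and show direction and rough size only.

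Two further inferences should not be drawn.
- A reader might put a minimum on the share of re-irradiated patients from the LRBC cohort. The protocol supports none: 15 LRBC patients among 55 would be 27%, Section 8 allows cohort sizes to vary, and 60 is an upper limit.
- A reader might suppose that a clean early safety result would drive the extension of recruitment. The criteria in Section 9 are recruitment, implementability and funding; safety is not among them.

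The mismatch between the synopsis endpoint (local SAEs) and Table 1 (local AEs and ARs) is a separate inconsistency. It leaves unclear what is to be collected even within the window.

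**What to change.** Amend Section 11 and the CRF:
- Record local AEs and SAEs at the treated site, graded by CTCAE v5.0, at the record reviews already in the schedule: 6 weeks, 12 weeks, progression and 12 months.
- Add toxicity to the items that Section 13 takes from the record.
- Report the period to 6 weeks and the later period separately, each with its own denominator of patients still under follow-up.
- For each later event, note any earlier local progression or systemic therapy.
- Reconcile the synopsis and Table 1 so that one safety endpoint applies throughout.

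If the sponsor keeps the present window, the objective and the final report should state that the safety conclusion covers only events up to 6 weeks after radiotherapy.

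The cost is a protocol amendment and one further CRF page at reviews that already take place. No visits are added and treatment is unchanged. The drawback is that later events will be harder to attribute once immunotherapy has started or the disease has progressed.
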